5.0 SELECTION AND WITHDRAWAL OF SUBJECTS

5.1 INCLUSION CRITERIA

- Histologically confirmed diagnosis of invasive cervical cancer
- Measurable Disease (RECIST 1.1)
- 0-1 prior chemotherapy regimens for recurrent or advanced disease. Platinum based chemotherapy administered as a radiation sensitizer agent is allowed and does not count as prior therapy
- Adequate organ function defined as:
 - bone marrow (AGC \geq 1,500, platelet \geq 100,000),
 - renal (serum creatinine $<$ 2.0 mg/dl)
 - hepatic function (bilirubin \leq 1.5 times the upper limit of the normal range (ULN), and alkaline phosphatase, alanine aminotransferase (ALT) and aspartate aminotransferase (AST) \leq 3 x ULN (in the case of liver metastases, \leq 5 x ULN).
- Peripheral neuropathy grade 0-2
- Recovery of all chemotherapy or radiation-related toxicities to Grade \leq 1, except for alopecia and peripheral neuropathy.
- Performance status 0-2
- Signed Informed Consent
- Patients \geq 18 years old

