History & Physical Exam	X	X			X	
Weight, Performance Status	X	X				
Toxicity Assessment		X Day 1 and 8				
WBC (differential), Hgb, platelets	X	X Day 1 and 8				
Electrolytes, MG, BUN, Cr	X	X				
LFT (Bilirubin, AST, ALT, Alkaline phosphatase		X				
EKG	X			X		
CXR	X		X ⁶			
Radiology, x-ray or Scans for disease measurement	X		X			
Tissue collection ³	X					
Peripheral Blood Collection for Correlative Studies		X ⁴				X
Eribulin		Day 1 and 8				

¹ Within 24 hrs² As clinically indicated³ From paraffin embedded prior biopsy⁴ Cycles 1-6⁵ Within 28 days of each cycle⁶ CXR is only required in the event that a CT of the chest is not done. Should a CXR be given in place of a CT scan, an additional CXR should be repeated every 2 cycles.

10.0**CRITERIA FOR EVALUATION AND ENDPOINT DEFINITIONS**

The outcome status (in terms of toxicity, response, reason off study, progression, and survival) of all eligible patients will be reported. All eligible patients who begin treatment will be included in the analysis of response, survival and time-to-failure.

Toxicities and adverse events including laboratory adverse events will be graded and summarized according to the National Cancer Institute CTCAE, v4.3 (available on the NCI website at: <http://ctep.cancer.gov/forms/CTCAEv4.pdf>).

Response will be evaluated according to the RECIST criteria v1.1:

Eligibility

Only patients with measurable disease (at least one measurable lesion) at baseline should be included in protocols where objective tumor response is the primary endpoint.

Measurable lesions - lesions that can be accurately measured in at least one dimension with longest diameter ≥ 10 mm and 2x slice thickness on CT scan. Lymph nodes must be ≥ 15 mm in **short axis**. Bone lesions may be measurable if there is a lytic/soft tissue component that meets minimum size criteria. CXR lesions must be > 20 mm.

Non-measurable lesions - all other lesions, including small lesions or lesions not conventionally measurable (i.e. leptomeningeal disease, ascites, pleural/pericardial effusion, inflammatory breast disease, lymphangitis cutis/pulmonis, cystic lesions, and also abdominal masses that are not confirmed) should be noted and followed by imaging techniques but not measured.

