- All measurements should be taken and recorded in metric notation, using a ruler or calipers. All baseline evaluations should be performed as closely as possible to the beginning of treatment and never more than 4 weeks before the beginning of the treatment.
- The same method of assessment and the same technique should be used to characterize each identified and reported lesion at baseline and during follow-up.
- Clinical lesions will only be considered measurable when they are superficial (e.g., skin nodules and palpable lymph nodes). For the case of skin lesions, documentation by color photography, including a ruler to estimate the size of the lesion, is recommended.

Methods of Measurement

CT and MRI are the best currently available and reproducible methods to measure target lesions selected for response assessment. Conventional CT and MRI should be performed with cuts of 10 mm or less in slice thickness contiguously. Spiral CT should be performed using a 5 mm contiguous reconstruction algorithm. This applies to tumors of the chest, abdomen and pelvis. Head and neck tumors and those of extremities usually require specific protocols.

Lesions on chest X-ray are acceptable as measurable lesions when they are clearly defined and surrounded by aerated lung. However, CT is preferable.

When the primary endpoint of the study is objective response evaluation, ultrasound (US) should not be used to measure tumor lesions. It is, however, a possible alternative to clinical measurements of superficial palpable lymph nodes, subcutaneous lesions and thyroid nodules. US might also be useful to confirm the complete disappearance of superficial lesions usually assessed by clinical examination.

Cytology and histology can be used to differentiate between PR and CR in rare cases (e.g., after treatment to differentiate between residual benign lesions and residual malignant lesions in tumor types such as germ cell tumors).

Baseline documentation of “Target” and “Non-Target” lesions

All measurable lesions up to a maximum of five lesions total (2 per organ), representative of all involved organs should be identified as ***target lesions*** and recorded and measured at baseline.

Lymph node measurements should reflect the **short diameter**

Target lesions should be selected on the basis of their size (lesions with the longest diameter) and their suitability for accurate repeated measurements (either by imaging techniques or clinically).

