A sum of the longest diameter (LD) for *all target lesions* will be calculated and reported as the baseline sum LD. The baseline sum LD will be used as reference by which to characterize the objective tumor.

All other lesions (or sites of disease) should be identified as ***non-target lesions*** and should also be recorded at baseline. Measurements of these lesions are not required, but the presence or absence of each should be noted throughout follow-up.

Response Criteria

Evaluation of target lesions

* Complete Response (CR):	Disappearance of all target lesions
* Partial Response (PR):	At least a 30% decrease in the sum of the LD of target lesions, taking as reference the baseline sum LD
* Progressive Disease (PD):	At least a 20% increase in the sum of the LD of target lesions, taking as reference the smallest sum LD recorded since the treatment started or the appearance of one or more new lesions
* Stable Disease (SD):	Neither sufficient shrinkage to qualify for PR nor sufficient increase to qualify for PD, taking as reference the smallest sum LD since the treatment started

Evaluation of non-target lesions

* Complete Response (CR):	Disappearance of all non-target lesions and normalization of tumor marker level
* Incomplete	Persistence of one or more non-target lesion(s) or/and

Response/
Stable Disease
(SD):

* Progressive
Disease (PD):

maintenance of tumor marker level above the normal limits

Although a clear progression of “non target” lesions only is exceptional, in such circumstances, the opinion of the treating physician should prevail and the progression status should be confirmed later on by the review panel (or study chair).

Evaluation of best overall response

The best overall response is the best response recorded from the start of the treatment until disease progression/recurrence (taking as reference for PD the smallest measurements recorded since the treatment started). In general, the patient's best response assignment will depend on the achievement of both measurement and confirmation criteria

Target lesions	Non-Target lesions	New Lesions	Overall response
CR	CR	No	CR
CR	Incomplete response/SD	No	PR
PR	Non-PD	No	PR
SD	Non-PD	No	SD
PD	Any	Yes or No	PD
Any	PD	Yes or No	PD
Any	Any	Yes	PD

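### Section 10.0 prints a target-lesion progression rule with no minimum absolute increase and does not say whether it or the named RECIST v1.1 governs, so patients with small nadir sums can be wrongly scored as PFS6 failures

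*Combined protocol and SAP*

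**What the plan says.** Section 10.0 opens its response criteria with "Response will be evaluated according to the RECIST criteria v1.1", and Section 5.1 cites the same version for measurable disease. Section 10.0 then writes the rules out. For target lesions, progression is "At least a 20% increase in the sum of the LD of target lesions, taking as reference the smallest sum LD recorded since the treatment" (that is, over the nadir sum); any new lesion also counts. This is the only numeric threshold for progression in the document. No minimum in millimetres appears anywhere.

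The same section accepts as measurable a non-nodal lesion with "longest diameter ≥ 10 mm and 2x slice thickness on CT scan"; nodes must reach 15 mm in short axis. On imaging it states: "Spiral CT should be performed using a 5 mm contiguous reconstruction algorithm". Conventional cuts may be up to 10 mm. The sum covers one to five target lesions.

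Partial and complete responses need a repeat assessment at least 4 weeks later, and progression in non-target lesions alone goes to a review panel or the study chair. Target-lesion progression needs neither. Section 10.1.1 ends PFS when progression is first observed. Section 13.0 makes PFS6 the primary endpoint and the basis of the 1/15 and 6/30 rules. Section 8.3 points to Section 10.1 for the definition of progression, but Section 10.1 gives no threshold.

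**The concern.** A purely relative threshold becomes very small in millimetres when the reference sum is small. Because the reference is the nadir, this can happen in a patient who started with a small sum or in one whose disease has shrunk. One unconfirmed reading then produces a PFS event.

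Naming RECIST v1.1 does not settle the matter, because the plan does not say what happens if the named criteria and the printed rule differ. Two assessors could score the same scan differently on the endpoint that drives both the interim stop and the final decision. A false progression call can only remove a PFS6 success, so it works against an active drug.

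**Working it through.** **1. The plan's own design figures.** Inputs from Section 13.0: continue if at least 1/15, success if at least 6/30, null rate 10%, alternative 26%. With X ~ Bin(15, p) in stage 1 and Y ~ Bin(15, p) in stage 2,

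P(success) = Σ over x = 1 to 15 of P(X = x) × P(Y ≥ 6 − x).

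At p = 0.10 this is 0.0727 (stated 0.072, which is this value truncated). At p = 0.26 it is 0.828 (stated at least 0.80). The design reproduces.

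**2. The threshold in millimetres.** Rise needed = 0.20 × nadir sum: 10 mm needs 2 mm, 15 mm needs 3 mm, 20 mm needs 4 mm, 25 mm needs 5 mm, 50 mm needs 10 mm.

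- The 2 mm case at baseline requires a sole 10 mm non-nodal lesion on slices of 5 mm or less (2 × 5 = 10). On 10 mm cuts the smallest CT lesion is 20 mm, and a sole node is at least 15 mm.
- After shrinkage, a lesion going 30 to 10 to 12 mm is (12 − 10)/10 = +20% from nadir and (30 − 12)/30 = 60% below baseline.
- An added minimum of 5 mm changes a call only when 0.20 × nadir < 5, that is, when the nadir sum is below 25 mm.

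**3. False progression under no true change.** Scans every two 21-day cycles (Section 9.0) are 6 weeks apart, giving about four by 6 months. Simulation: baseline plus four scans, constant true sum, independent normal error on each sum, progression judged against the running nadir. The error SD is an assumption. Cells show the percentage scored as progressed, printed rule / with a 5 mm minimum.

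| True sum | SD 0.5 mm | SD 1.0 mm | SD 1.5 mm |
|---|---|---|---|
| 10 mm | 4 / 0 | 50 / 0.2 | 74 / 7 |
| 15 mm | 0.1 / 0 | 18 / 0.2 | 50 / 7 |
| 20 mm | 0 / 0 | 4 / 0.2 | 27 / 7 |
| 25 mm | 0 / 0 | 0.6 / 0.2 | 12 / 7 |
| 30 mm | 0 / 0 | 0.1 / 0.1 | 4 / 4 |

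At SD 0.75 mm a 10 mm sum gives 27 / 0. At SD 2 mm it gives 85 / 25.

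The printed rule depends only on the ratio of sum to SD. A 40 mm sum at SD 1.5 mm (ratio 26.7) therefore lies between the 25 mm and 30 mm rows at SD 1.0, that is, between 0.1% and 0.6%.

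**4. Effect on the test, for illustration.** If a share f of true successes were scored as progressed, p becomes p(1 − f).

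- f = 5%: 0.26 × 0.95 = 0.247, power 0.785; 0.10 × 0.95 = 0.095, type I error 0.059.
- f = 10%: 0.26 × 0.90 = 0.234, power 0.734; 0.10 × 0.90 = 0.090, type I error 0.048.

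At SD 1.0 mm, f = 5% would need about 10% of successes to have a 10 mm sum (0.10 × 0.50 = 0.05), or about 27% to have a 15 mm sum (0.27 × 0.185 = 0.05). At SD 0.5 mm, even if every success had a stable 10 mm sum, the loss would be 4%.

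**The case against.** The strongest reply is that RECIST v1.1 is named in Sections 5.1 and 10.0, so assessors may apply the named criteria and not the printed sentence alone. That stands as a limit on how often the printed rule would be followed. It does not remove the ambiguity, because the plan supplies only one numeric threshold and no order of precedence. A reader might go further and infer that the printed rule misquotes RECIST v1.1. The documents do not reproduce those criteria, so that inference is not relied on here.

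The case is also narrow. The rule applies to the sum of up to five lesions, and a 10 mm baseline sum requires one minimum-size lesion. Slice thickness is not a measure of in-plane diameter error, so the documents do not establish that 2 mm is within measurement error.

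The simulation is sensitive to its assumptions. For a 10 mm sum at SD 1.0 mm, requiring the baseline reading to be at least 10 mm lowers 50% to 38%. If half the error variance were instead shared across a patient's scans, it would fall to 23%. These points limit the size of the problem but leave the mechanism in place.

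Finally, Section 13.0 does not say which progression rule lies behind the 10% benchmark. A more lenient rule may therefore not be neutral against it. This stands, and is a reason to fix the definition before the data are scored.

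**Conclusion.** The point holds as a gap in the primary-endpoint definition. The printed rule allows a 2 mm rise in a small nadir sum, read once, to make a patient a PFS6 failure, and the plan does not say whether that rule or the named criteria governs. Exposure is mainly at nadir sums below about 25 mm. Between 25 mm and 40 mm some false calls remain possible if error is large, but a 5 mm minimum would not prevent them.

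The size is unknown. The 4% to 74% range for a stable 10 mm sum rests on assumed independent errors of SD 0.5 to 1.5 mm. The power figures rest on an assumed share of lost successes.

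A reader might infer that small-volume patients are in fact being misclassified, or that the trial falls below its stated power of 0.80. Neither follows, because the documents give no measurement error, no baseline or nadir sums, and no evidence of which rule assessors apply. Nor does the flaw make a false positive trial more likely: under this mechanism type I error falls.

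**What to change.** For scoring PFS, PFS6 and BOR, add to the target-lesion progression definition in Section 10.0 a minimum absolute increase in the sum, required together with the 20% rise over nadir. Leave new lesions as a separate route to progression. A minimum of 5 mm is one option, since it equals one spiral CT slice as stated in the plan; the documents themselves supply no value. State that this reconciled definition governs over any conflicting text, including the general reference to RECIST v1.1.

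This costs one clause and one sentence. It needs no extra scans or patients, and N = 30 and the 1/15 and 6/30 rules are unchanged. The downside is that true progression in very small disease may be scored about one scan, or 6 weeks, later.

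Separately, the sponsor should reconcile the Section 8.3 pointer to Section 10.1 with the text of Section 10.0, because Section 10.1 contains no threshold. No treatment rule is proposed here.

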10.1 ENDPOINT DEFINITIONS

10.1.1 PRIMARY EFFICACY ENDPOINT

Progression-free survival is defined as the time from first day of treatment to the first observation of disease progression or death due to any cause. If a patient has not progressed or died, progression-free survival is censored at the time of last follow-up.

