8.3 TREATMENT REMOVAL

Patients will be removed from treatment in the event of:

- Peripheral neuropathy Grade >2 that does not improve as in Section 8.1
- Grade 3 or 4 hypersensitivity/infusion reaction.
- Inability of subject to comply with study requirements.
- Determination by the investigator that it is no longer safe for the subject to continue therapy.
- Progression of disease (as defined in Section 10.1).
- Delay of treatment \geq 2 weeks.
- Patient may choose to withdraw her participation at any time for any reason

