10.1.2 SECONDARY EFFICACY ENDPOINTS

The best overall response is the best response recorded from the start of the treatment until disease progression/recurrence (taking as reference for PD the smallest measurements recorded since the treatment started).

Overall survival is defined as the time from first day of treatment to time of death due to any cause. If a patient is still alive, survival time is censored at the time of last follow-up.

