13.0 STATISTICAL CONSIDERATIONS

Study Design: This is a two-stage, single arm study to obtain preliminary evidence of efficacy of Eribulin in the treatment of recurrent cervical cancer. Current chemotherapy treatments for recurrent cervical cancer are associated with response rates and 6-month progression-free survival rates no higher than 10%. The objective of this study is to determine whether there is evidence that treatment with Eribulin will result in response and 6-month PFS rates that exceed 10%, suggesting promising activity and encouraging further study.

The primary efficacy endpoint will be 6-month progression-free survival (PFS₆). The secondary efficacy endpoint will be best overall response (BOR). A total of 30 patients who are fully evaluable for PFS₆ will be enrolled on this study. Patients who are not fully evaluable for PFS₆ will be replaced. Replaced patients will nonetheless be included in the final efficacy analysis. PFS₆ will be the endpoint for interim monitoring.

An interim analysis will occur when 15 patients have been evaluated for PFS₆, with final analysis once 30 patients have been evaluated for PFS₆. $\geq 1/15$ patients who achieve PFS₆ are required to continue study accrual to 30 patients. $\geq 6/30$ patients who achieve PFS₆ will be considered sufficient evidence of efficacy to warrant further study. The study will be terminated if fewer than 1/15 patients are progression-free at 6 months. The study may remain open pending the interim results on the first 15 patients, but will be suspended to enrollment if the 20th patient is enrolled before the interim results are available.

Sample size justification. This design has one-sided Type I error of <0.10 (0.072) for a true PFS₆ rate of 10%, and power of at least 0.80 for a true PFS₆ rate of 26%. Hence this study has sufficient power to detect moderate and clinical important improvements in PFS₆ rate due to Eribulin treatment when compared to past experience with chemotherapy treatment of recurrent cervical cancer.

Additional efficacy analyses. Product limits estimates of 6-month PFS will be computed using all patients enrolled on the study. 95% confidence intervals will be based on Greenwood standard errors. In addition, exact 95% binomial confidence intervals will be compute for the BOR rate.

Toxicity analyses. The rate of Grade 3+ hematology and non-hematologic toxicities will be computed for course 1 and for all courses combined.

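### No rule covers anticancer treatment started before progression, so disease control or response on another therapy can count towards eribulin's PFS6 and best response

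*Combined protocol and SAP*

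**What the plan says.** Section 10.1.1 measures progression-free survival from the start of treatment "to the first observation of disease progression or death due to any cause". The only censoring rule is "If a patient has not progressed or died, progression-free survival is censored at the time of last follow-up".

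Section 10.1.2: "The best overall response is the best response recorded from the start of the treatment until disease progression/recurrence". Section 10.0 uses the same window and adds that a partial or complete response must be confirmed at least 4 weeks after the criteria are first met.

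Section 8.3 begins "Patients will be removed from treatment in the event of" and lists several reasons besides progression, among them "Grade 3 or 4 hypersensitivity/infusion reaction" and "Patient may choose to withdraw her participation at any time for any reason". The others are unresolved neuropathy, non-compliance, investigator judgement and a treatment delay of 2 weeks or more. Section 8.2 adds discontinuation after a further qualifying event at the lowest dose level.

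Section 13.0 makes PFS6 the primary endpoint. At least 1 of 15 is needed to continue, and at the end six or more of 30 "patients who achieve PFS₆ will be considered sufficient evidence of efficacy to warrant further study". Patients not fully evaluable for PFS6 are replaced but stay in the final efficacy analysis; full evaluability is not defined.

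Other anticancer treatment appears only as history before entry (Sections 5.1 and 5.2). Section 7.1 covers growth factors, steroids, H1/H2 blockers and antiemetics. No section makes later anticancer therapy an event, a censoring point, a reason for non-evaluability or the subject of a sensitivity analysis.

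**The concern.** The definitions keep the PFS and best-response clocks running after eribulin stops, whatever is given next. Consider a patient who leaves eribulin at month 2 for toxicity, starts another regimen or pelvic radiotherapy, and is known to be free of progression at month 6. Nothing in Section 10.1.1 prevents her from being one of the six successes. If she first reaches a confirmed partial response on the other treatment, nothing in Section 10.1.2 stops that response being counted for eribulin.

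Section 13.0 asks whether eribulin gives rates above 10%. With no control arm, all observed PFS6 is attributed to the study drug, so control borrowed from another therapy pushes the result in one direction only. The same outcomes feed the Cox and logistic models for the correlative markers.

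**Working it through.** **Inputs.** From Section 13.0: 15 + 15 patients; continue if at least 1 of 15; success if at least 6 of 30; null rate 10%; stated one-sided type I error 0.072 with a limit of 0.10; stated power at least 0.80 at 26%.

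**Step 1: reproduce the plan's figures.** For an apparent PFS6 rate p, with X1 and X2 independent Binomial(15, p),

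P(success) = Σ over x = 1 to 15 of P(X1 = x) × P(X2 ≥ 6 − x).

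This gives 0.0727 at p = 0.10 (the stated 0.072 is that value truncated) and 0.828 at p = 0.26. The design reproduces.

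**Step 2: sensitivity to extra successes.** Hold the rate due to eribulin at 10% and let the apparent rate rise:

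| Apparent rate | P(success) |
|---|---|
| 10% | 0.073 |
| 11% | 0.104 |
| 13.3% (on average one extra success in 30: 0.10 + 1/30) | 0.202 |
| 15% | 0.288 |
| 20% | 0.570 |

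One percentage point is enough to pass the plan's 0.10 limit.

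**Step 3: link to switching.** The documents give no switching rate, so two quantities are assumed. Let f be the share of all patients who stop eribulin without progression, start another therapy before 6 months and would otherwise have failed. Let s be the share of those who are progression-free at 6 months on the other therapy. Then p = 0.10 + f × s; for example, f = 10% and s = 25% give p = 0.10 + 0.025 = 0.125.

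| f | s = 10% | s = 25% | s = 50% |
|---|---|---|---|
| 5% | 0.088 (p = 0.105) | 0.113 (p = 0.1125) | 0.164 (p = 0.125) |
| 10% | 0.104 (p = 0.11) | 0.164 (p = 0.125) | 0.288 (p = 0.15) |
| 20% | 0.142 (p = 0.12) | 0.288 (p = 0.15) | 0.570 (p = 0.20) |

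Only the mildest cell stays under 0.10.

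**Step 4: cost of counting switchers as failures.** If that lowers the rate under the alternative, the Step 1 formula gives power 0.828 at 26%, 0.795 at 25% and 0.758 at 24%. A loss of one point already takes power just below the planned 0.80.

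**The case against.** The strongest reply is that this is an omission and that other provisions limit its effect. Four points deserve weight.

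- **Confirmation.** A reader might infer that any 30% shrinkage on another therapy makes the patient an eribulin responder. Section 10.0 does not support that: the response must be confirmed by repeat assessment. A confirmed response on the other therapy would still count.
- **Assessment schedule.** A reader might infer that the problem arises even with every scheduled scan done. The Section 9.0 calendar ties scans to every 2 cycles and lists only history and physical examination at the 3-monthly follow-up. A patient off eribulin at month 2 has no month-6 scan scheduled, and the Section 10.0 request to keep documenting progression concerns symptomatic deterioration and sets no timetable. This makes the path less automatic, above all for response, but does not close it.
- **Evaluability.** A reader might infer that the rules definitely count such a patient as a success. They do not settle it, because an undefined evaluability criterion could be used to replace her. Since replaced patients stay in the final efficacy analysis, the gap remains.
- **Size.** The grade 3 or higher incidences in Section 4.0 (neuropathy 8%, fatigue 10%) are not stopping rates, since Section 8.2 provides for delay and reduction before discontinuation; they cannot serve as a guide to f. Section 1.0 puts 6-month PFS after platinum at about 10% at best, so a low s is plausible. A higher s is also plausible: these patients are selected as not yet progressed, and Section 5.1 admits patients with no prior regimen for recurrent or advanced disease, for whom cisplatin, which Section 1.0 calls the most active agent, may be unused.

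Following patients regardless of later therapy is also a legitimate strategy when stated and justified. Here it is neither. How the 10% benchmark handled later therapy cannot be seen from the documents.

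**Conclusion.** The concern holds as a gap in the endpoint rules. The wording of Sections 10.1.1 and 10.1.2 can credit another therapy's effect to eribulin, and nothing elsewhere rules this out. The direction is certain, since any error favours the drug. The size is not: 0.088 to 0.57 against a nominal 0.073, resting wholly on the assumed f of 5 to 20% and s of 10 to 50%. What does not depend on those assumptions is how little slack the decision rule has, with the 0.10 limit passed at an apparent rate of 11%. A reader might go further and infer that one or two switchers would turn a negative trial positive. That is so only if the count without them is 4 or 5 of 30, and the documents give no basis for expecting it. The change should be made, because the gap reaches the primary decision and is cheap to close.

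**What to change.** 1. In Section 10.1.2, and in the matching text of Section 10.0, end the best-response window at progression or at the start of non-protocol anticancer treatment (systemic therapy, or radiotherapy or surgery to a tumour lesion), whichever comes first.
2. In Sections 10.1.1 and 13.0, state before data are seen how a patient who starts such treatment before 6 months without progression is classified in the 1/15 and 6/30 decisions. Count her as not achieving PFS6 in the primary decision or, at the least, in a prespecified sensitivity analysis. Say whether she is fully evaluable. Report the product-limit estimate both with the start of that treatment as an event and with censoring at the last tumour assessment before it, so that the estimate can be read consistently with the decision rule.
3. Record the type and start date of the treatment on the existing Response/Off-Study/Follow-Up Form.

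The cost is a few sentences and a small addition to one form; study treatment and the sample size of 30 do not change. Observed PFS6 and response may be lower, and some patients who switch for toxicity while still benefiting would count as failures. If failure is the primary rule, the power loss in Step 4 should be acknowledged in Section 13.0.
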